### 3.0 Objectives

**Aim 1: Elucidate merits of transdiagnostic sampling.** Within the two intervention groups (Group 1: n = 24, Active iTBS and Active iTBS + APT; Group 2: n = 24, Placebo iTBS and Placebo iTBS + APT), we expect that (1i) neurologic diagnosis (stroke, TBI) will not moderate the effect of Active iTBS or Active iTBS + APT on Maximum Cognitive Gain as assessed by the Modified Digit Span (MDS) and the Streamlined AMPS (AMPS).

**Aim 2: Obtain pilot data to inform estimation of treatment and practice effects.** We will gather pilot data regarding the magnitude and duration of treatment effects as well as MDS and AMPS practice effects. As we anticipate (2i) greater immediate gains in IADL performance (AMPS) after Active iTBS + APT when compared to Active iTBS alone, we will compare Maximum Cognitive Gains (MCG) on MDS with MCG on AMPS between the Active iTBS and Active iTBS + APT groups to determine if MCGs differ in magnitude. We will also determine if

Active iTBS + APT trend lines indicate an additive treatment effect of APT on MDS and/or AMPS. We also anticipate (2ii) some persisting treatment effects and to explicate these effects we will examine effects for Active iTBS and Active iTBS + APT in the short-term (post-pre-treatment), long-term (2 weeks after a session) and cumulatively across treatment sessions. Since the AMPS uses a unique task during each testing interval and MDS uses 1 of 6 alternate test forms, we will determine (2iii) presence and magnitude of practice effects by testing whether prior exposure to MDS or AMPS results in MDS or AMPS gains for Placebo iTBS.

**Aim 3: Explicate study attrition by perceived suitability of aspects the study design and the relationship between this perceived suitability and fatigue as well as mood.** We will test the ideas that (3i) Attrition rates do not differ by stroke and TBI groups, (3ii) Veterans across stroke and TBI have similar perceptions regarding suitability of the number and type of tests as well as number of study-days, and (3iii) perceived suitability is related to Veteran-reported fatigue and mood.

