**Figure 1. Four Step Screening Process: Summary of Exclusion Criteria by Steps**

For this within-subject placebo-controlled partially-blinded treatment protocol (Fig 2), we will enroll 48 medically stable Veterans with stabilized recovery trajectories after a stroke or a TBI and who have a homogeneous level of moderately impaired cognitive function persisting after standard rehabilitation.

An equal number of Veterans with stroke/TBI (24-stroke; 24-TBI) will be enrolled, but we will over-sample females (Figure 2). For each iTBS group to include an equal number of Veterans with stroke/TBI, Veterans will be randomly assigned by diagnostic groups, to receive Active iTBS or Placebo iTBS. To measure immediate effects (ImE), an equal number of Veterans with stroke/TBI within each iTBS group will be randomly assigned to be tested with the Modified Digit Span (MDS) or AMPS, three times at 30 min intervals. Persisting effects (PE) tests will be administered to all participants at five timepoints including prior to and after Active iTBS or Placebo iTBS and 2-weeks later prior to the 2nd intervention, where all Veterans receive APT paired with their assigned iTBS (Active iTBS + APT or Placebo iTBS + APT). The alternate ImE test is then administered three times at 30 min intervals, followed by re-administration of all PE tests. Two weeks later, all PE tests are administered a 5th time (B4). ImE and PE measures are used to define magnitude and duration of cognitive change. Randomization (SAS Proc Plan) will be managed by one un-blinded researcher who will not provide interventions or conduct testing.

**Figure 2. Study Design (ImE = Immediate Effects Tests; AMPS = AMPS or MDS = Modified Digit Span; PE = Persisting Effects Tests for all participants; Study Day-1: Obtain Covariates and Treatment preparation information; B0 = Pre-Study-Day-2; B1 = Post-Study-Day-2; After 2-Weeks B2 = Pre-Study-Day-3; B3 = Post-Study-Day-3; After 2-Weeks B4 = Study-Day 4)**

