#### **Potential Risks:**

**Physical:** The experimental intervention of iTBS being provided is a patterned form of rTMS. The biggest concern for transcranial magnetic stimulation (TMS) is seizure induction. Other known side effects of rTMS include headache, dizziness, tinnitus, nausea, neck pain, or scalp burns. Side effects reported to date for iTBS include sweating, feeling dizzy, neck pain, mild decrease in diastolic blood pressure, headache, discomfort/mild tingling sensation, occasional local pain or discomfort during stimulation, and isolated, transient, non-pulsatile, left-sided tinnitus. Additionally, there is risk of equipment malfunction. The Magventure MagProX100 with MagOption stimulator and Magpro Cool Coil B65 or one of the coils may malfunction which may result in harm to the patient.

Participation in the AMPS requires the Veteran to complete a variety of physical tasks that may be challenging to complete. There is a risk of injury depending on the type of task the Veteran identifies as valuable to complete (e.g. burns, laceration, falls).

**Psychological:** Participation in the study outcome measures, including self-report (i.e. PCL), observational (i.e. ABS), neuropsychological (i.e. DKEFS, WAIS-IV), cognitive capacity and function outcomes (i.e. AMPS, RBANS), effort testing (i.e. DCT) structured interview data (AMPS) and safety outcomes (Data Safety Monitoring Scale), involves minimal risks and discomforts. The risks for the Veteran include frustration, agitation, anxiety, fatigue, and possible trigger of PTSD symptoms.

**fMRI:** There are no known risks associated with fMRI when individuals are appropriately screened, except some people have experienced discomfort in trying to remain still. MRI is not safe when specific ferromagnetic materials are present in the body (i.e. metal fragments in brain/skull, metal surgical clips, etc). Some people have been noted to be anxious or claustrophobic during the scan. The MRI scanner makes loud banging noises during scanning.

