For Aim 3, we will compute study attrition as percent of participants dropping out after Study-Day 2 and after Study-Day 3. We will examine whether or not these attrition rates differ (3i) by stroke and TBI groups using chi-square. To examine if Veteran's with stroke and TBI have (3ii) different perceptions regarding the suitability of the number and type of tests and number of study-days, we will compare each group's average ratings, by suitability index, using t-tests. To explore the relationship between perceived suitability and fatigue as well as mood (3iii), we will compute Pearson correlations at each of the 5-timepoints (B0 through B4) between average ratings of suitability indices 1 through 3 and averages for each of the two fatigue measures and each of the five mood measures [5x (3x2) + 5x (3x5) = 105 correlations]. We will also compute correlations for average suitability indices 7 through 8 collected on Study-Day 4 (B4) with the averages from that same day for each of the two fatigue measures and each of the five mood measures [1x (2x2) + 1x (2x5) = 14 correlations]. We will test the significance of each correlation using Fisher Z test and results will be interpreted accordingly.

Aims 2 and 3 involve multiple comparisons. Bonferroni correction of type I error rate is very conservative, and, at this early research stage, it could mask important findings. Thus, we will control for false discovery rate (FDR) using an FDR level of .05.

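### Aim 3iii correlates suitability with fatigue and mood across all Veterans without allowing for diagnosis or randomised arm, so a factor that shifts both could create or mask a Veteran-level relation; consider adding adjusted correlations.

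*Combined protocol and SAP*

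**What the plan says.** Section 3.0 gives the idea to be tested as "3iii) perceived suitability is related to Veteran-reported fatigue and mood". Section 5.6 then sets out the analysis: "we will compute Pearson correlations at each of the 5-timepoints (B0 through B4", between suitability items 1 to 3 and two fatigue and five mood measures. It counts these as "5x (3x2) + 5x (3x5) = 105 correlations". Items 7 and 8 are correlated with the same measures at B4 only, counted as "1x (2x2) + 1x (2x5) = 14 correlations". On testing it says "We will test the significance of each correlation using Fisher Z test". Multiplicity in Aims 2 and 3 is handled by false discovery rate control, "using an FDR level of .05".

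The design in Section 5.1 has 24 Veterans with stroke and 24 with TBI, and "Veterans will be randomly assigned by diagnostic groups, to receive Active iTBS or Placebo iTBS". Section 3.0 gives 24 per arm.

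The text on 3iii mentions no stratification, partial correlation or covariate. The covariate statements elsewhere (the medical-record review in 5.1, and Table 3 in 5.5) do not list arm or diagnosis as adjustment variables and are not tied to 3iii.

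**The concern.** The plan does not state that the groups are pooled. That is inferred from the counts, which have no multiplier for two arms or two diagnoses, and from the absence of any adjustment. The inference is firm.

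The plan itself leaves open whether groups differ on both sides of these correlations. Aim 3ii compares suitability ratings between stroke and TBI. Aim 2ii compares every persisting-effects measure between Active and Placebo, and Table 2 places the fatigue and mood scales in that battery. If a group is both more fatigued and less satisfied with the tests, an unadjusted correlation is non-zero even when fatigue and satisfaction are unrelated among Veterans within each group. If the shifts run against the true relation, the correlation shrinks. In either case the pilot could misdescribe how a Veteran's fatigue or mood relates to his or her view of the test burden.

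**Working it through.** **1. The plan's counts.** Items 1 to 3: 5 × (3 × 2) + 5 × (3 × 5) = 30 + 75 = 105. Items 7 and 8: 1 × (2 × 2) + 1 × (2 × 5) = 4 + 10 = 14. Both reproduce, and the total is 119. Separate coefficients in the four arm-by-diagnosis cells would have given 4 × 119 = 476. So there is one coefficient per pair and time point, over all Veterans.

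**2. Inputs.** From the documents: n = 48, in a balanced 2 × 2 layout with 12 per cell; about 42 after the 12% attrition in 5.6; Fisher Z test (two-sided 0.05 assumed, since sidedness is not stated). Assumed: shifts of 0.35 to 1.0 within-group SD, a range that includes the small, medium and large effect sizes in 5.6 (0.35, 0.60, 0.90); within-group r of 0 or 0.40.

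**3. Formula.** For one 1:1 factor shifting the two variables by d1 and d2:

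r_pooled = (r_within + d1·d2/4) / √[(1 + d1²/4)(1 + d2²/4)]

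For two balanced factors with the same shifts, the d1·d2/4, d1²/4 and d2²/4 terms double. At n = 48 the critical |r| is tanh(1.96/√45) = 0.284.

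**4. Creating a relation (r_within = 0).** Rejection rates come from at least 20,000 simulated trials per scenario, at 0.05 per test and before false discovery rate control.

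| Shift in both variables | Factors | r_pooled | Significant, unadjusted |
|---|---|---|---|
| 0.35 | one | 0.031/1.031 = 0.03 | 5.5% |
| 0.60 | one | 0.09/1.09 = 0.08 | 9% |
| 0.80 | one | 0.16/1.16 = 0.14 | 15% to 16% |
| 0.90 | one | 0.2025/1.2025 = 0.17 | 21% |
| 1.00 | one | 0.25/1.25 = 0.20 | 28% to 29% |
| 0.60 | two | 0.18/1.18 = 0.15 | 18% |
| 0.80 | two | 0.32/1.32 = 0.24 | 40% |

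Adjusted for arm and diagnosis, the rate is about 5% in every row.

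**5. Masking a relation (r_within = 0.40).** Opposing shifts from one factor:

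- 0.60 SD: r_pooled = (0.40 − 0.09)/1.09 = 0.28; detection about 51%.
- 0.80 SD: (0.40 − 0.16)/1.16 = 0.21; detection 28%.
- 0.90 SD: (0.40 − 0.2025)/1.2025 = 0.16; detection 18%.

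The adjusted test detects the relation in about 80% of trials throughout. With no shifts at all, detection is 82% unadjusted and 80% adjusted.

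**6. Limits of the effect.** A 0.90 SD shift in only one variable creates nothing (5% rejection). It dilutes r = 0.40 to 0.40/√1.2025 = 0.365, with detection of 73%. At n = 42 and one factor, 0.90 SD in both variables gives 19% false positives, and opposing 0.90 SD shifts leave 16% detection.

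**7. Mediation.** Suppose arm shifts fatigue by 0.8 SD and affects ratings only through fatigue, with r_within = 0.40. The unadjusted test detects the relation in 87% of trials and the adjusted test in about 80%. Here the unadjusted coefficient is not misleading, and adjustment gives up part of a genuine relation.

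**The case against.** The distortion needs the same factor to move both variables, and by a good deal. The documents give no such shift, and at 0.5 SD in one factor the rate is only about 7%. This stands.

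The route through arm is weakly supported. Items 1 to 3 rate the tests and items 7 and 8 the visits; none rates the stimulation. iTBS is double-blinded and both arms follow the same testing schedule. The risk text begins "Side effects reported to date for iTBS include sweating, feeling dizzy", and its list includes neither fatigue nor low mood; fatigue is attributed there to the outcome testing. One fatigue score covers the prior week, so a same-day session could hardly move it. At B0 randomised arms can differ only by chance. A reader might infer that the protocol expects iTBS to shift fatigue or mood because fatigue is tracked as a safety indicator. Tracking it is not evidence of an arm difference.

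Diagnosis is less easily dismissed. The plan expects similar ratings in stroke and TBI, and if that is true, diagnosis can only dilute a relation. But a non-significant 3ii result would not establish it: by the plan's own figures, 42 per group are needed to detect 0.60 SD, and there are 24.

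The rates above are not the plan's operating characteristics, because false discovery rate control comes on top. At the strictest Benjamini-Hochberg step for 119 tests (0.05/119), the one-factor 0.8 SD scenario rejects in about 0.5% of trials and the two-factor scenario in about 3%. These are lower bounds, since the step relaxes when other tests show signal. The procedure addresses multiplicity and does not remove the group shift from the coefficient.

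Finally, an unadjusted association across a deliberately transdiagnostic sample is a legitimate descriptive quantity. That is a reason to keep it on show, but it does not answer the Veteran-level question.

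**Conclusion.** The point holds in a limited form and is worth considering; it is not essential. The planned 3iii correlations take no account of two design factors that the plan elsewhere tests for differences in ratings and in fatigue and mood. The effect is negligible to small below about 0.6 SD in one factor. It becomes material at 0.8 SD or more, or when both factors act. This rests on assumed shifts, n = 48 and a per-test level of 0.05 before false discovery rate control. Diagnosis is relevant at all time points, arm only from B1 on, and an arm effect carried wholly by fatigue or mood is part of the relation that 3iii asks about.

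Two stronger readings are not supported. A reader might infer that the redesign of the test burden turns on this result. Section 5.6 describes the analysis as exploring a relationship and attaches no decision rule to it, and the Abstract lists suitability, fatigue and mood among the feasibility inputs to the future study. A reader might also infer that one mixed model over all visits would be an equivalent replacement. It would not: with a random intercept its single slope blends within- and between-Veteran association and assumes the same relation at every visit. Separate correlations by visit are a defensible choice.

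**What to change.** Add to the 3iii paragraph of Section 5.6 that, at each time point, partial correlations adjusted for diagnosis and iTBS arm will be reported beside the unadjusted Pearson correlations, and that the Veteran-level interpretation of 3iii will rest on the adjusted ones. Test each by Fisher z with √(n − 5) in place of √(n − 3), where n is the number of Veterans with both values at that time point. State that the false discovery rate procedure for 3iii is applied to the adjusted set, so that the number of tests is unchanged.

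Separate estimates in the four arm-by-diagnosis cells are not advised: with 12 Veterans per cell the critical |r| is 0.57.

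The cost is a few lines of text and two degrees of freedom, about two points of power at r = 0.40 (82% to 80%) if there are no group shifts. Both factors are already recorded. The adjusted coefficient also gives up any association that runs from arm through fatigue or mood to ratings; showing the unadjusted value alongside lets the reader see it.

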## Abstract

The purpose of this SPiRE is to identify the supports and barriers to scalability of Veteran-tailored iTBS and APT across neurologic conditions, with the longer-term goal of providing an empirical basis for the tailoring of a broader range of cognitive rehabilitation strategies to optimize each Veteran's cognitive function in daily life. After Veterans receive standard cognitive rehabilitation, cognitive impairments often persist and if they do make gains there is limited carry-over to daily function. The tenets of precision neurorehabilitation suggest that tailored interventions will optimize gains and carry-over, but precision-tailoring of cognitive rehabilitation will only be possible if researchers develop and test scalable approaches for identifying, organizing, and analyzing the multitude of Veteran-specific variables driving and influencing treatment responsiveness. This project addresses long-standing scientific barriers to understanding treatment responsiveness, particularly study sample heterogeneity and individual variability. We address study sample heterogeneity by linking Veterans, across TBI and ischemic stroke, according to levels of cognitive impairment. We create a cohort of Veterans with a homogeneous level of cognitive impairment, thereby enabling explication of person-centric factors influencing treatment responsiveness and carry-over to daily function. Advancing understanding of the basic study design elements will be achieved by leveraging our knowledge of intermittent Theta Burst Stimulation (iTBS) and iTBS paired with Attention Processing Training exercises (iTBS + APT). iTBS is advantageous as it robustly improves working memory with just one treatment session. These interventions, together, are advantageous as they can each be tailored to a Veteran's unique cognitive challenges and to target the neural site, unique to each Veteran's neuropathology. These two interventions also directly address cognitive deficits, while simultaneously inducing neuroplasticity in neural regions hampered or impaired by neural injury. We will study Veterans with moderately impaired cognition who, after standard cognitive rehabilitation, continue to struggle with daily life requiring assistance with complex instrumental activities of daily living (IADL). Veterans will participate in a series of two within-subject treatment studies, conducted on two separate days, 2-weeks apart. Veterans will be randomly assigned to first receive a single session of Active iTBS or Placebo iTBS and then they will receive APT paired with their assigned iTBS (Active iTBS + APT vs Placebo iTBS + APT). We will test if diagnosis moderates the effects of these interventions on both immediate and persisting change in cognition. For immediate effects, we use a novel testing battery and for persisting gains we use established and feasible neuropsychological tests as well as an established test of cognitive function during IADL. Results will be used to obtain pilot data and examine feasibility in terms of study attrition relative to Veteran fatigue, mood, and Veteran reports of suitability of key aspects of the study design. These findings will be used to develop a future merit within-subject cross-over study examining the overarching hypothesis that tailored iTBS and APT applied to a transdiagnostic sample and subsequently matched to a Veteran, according to a biotype algorithm, will result in better functional performance of Veteran-valued IADL.

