**Study-Day 1 (~5 hours) (may occur over 2 days):**

- 1. Complete tests/questionnaires that are not repeated. Some are collected for use as covariates (Table 2) and some are needed for treatment preparation.
  - a. Baseline testing battery
  - b. APT Baseline
  - c. fMRI-to be completed at NU CTI
  - d. Motor Threshold
  - e. Baseline EEG\*
- 2. Rating suitability of the number and types of tests 1-3.

\*EEG to be completed prior and reviewed by physician prior to Motor Threshold

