**Study-Day 2 (4 days after Study Day 1)(~8 hours):**

- 1. PE testing battery
- 2. A single session of **Active** iTBS or **Placebo** iTBS
- 3. Randomly assigned ImE test (MDS or AMPS), administered 3-times at 30 min intervals, each interval includes 5 to 15 min of rest).
- 4. PE testing battery
- 5. Suitability ratings 1-3

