**Study-Day 4 (2 weeks after Study-Day 3) (~2.5 hours):**

[figure not shown]
- 1. PE testing battery
- 2. Suitability rating 1-8

**Optional Study for Participants with diagnosis of TBI only- Day 5 (to occur within 2 weeks of Day 4, can occur on same day as Day 4) (~2 hours)**

- 1. Single session of Active iTBS at GIMME site of stimulation
- 2. ImE test: MDS, one time only
- 3. ImE test: AMPS, one time only

### Figure 3. Study Procedures by Study-Days 1 thru 4

ImE = Immediate Effects Tests; s-AMPS = Streamlined AMPS or MDS = Modified Digit Span; PE = Persisting Effects Tests for all participants

**Interventions.** All iTBS sessions will be **double-blinded**, but APT exercises **will not be blinded**. For **Active** iTBS and **Placebo** iTBS, the left DLPFC using the Resting Network Mapping algorithm.

**fMRI (neuroimaging)-** Functional MRI (fMRI) measures will be collected at Baseline. The fMRI measures will include structural imaging, 20 minutes of resting-state fMRI, diffusion tensor imaging (DTI) and an Arterial Spin Labelling Sequence (ASL). Participants will be in the MRI for approximately 55 minutes. fMRI scanning, for all participants, will take place at Northwestern University's CTI in the Olsen Pavilion located at [name].

Veterans will be responsible for transportation to the CTI, however parking vouchers will be provided at no cost to the participant. Parking is available at the Northwestern Memorial Hospital parking garage located across from the Olsen Pavilion. Research staff will be present on day of scan and available to provide assistance.

Scanning will take place on a Siemens Prisma 3.0 T MRI scanner equipped with a 64-channel head/neck coil. A high-resolution 3D MP-RAGE T1-weighted sagittal anatomical scan (voxel size = 0.8 mm isotropic resolution; 224 sagittal slices) will be collected for each participant. Resting state BOLD data will be collected using T2\* weighted EPI with a TR=0.5s, TE=25ms, flip angle of 48°, and 2mm isotropic voxels and a multiband factor of 8. Rest data will be collected while the subject views a fixation crosshair. The DTI data will use a two shell (64 directions per shell) acquisition with diffusion values of 1000 mm^2/sec. The acquisition will collect 1.5mm isotropic voxels with a TR=4500, TE=62ms and a multiband factor of 4, and 96 slices.

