**Table 4. Indices of Suitability**

1. The tests were all appropriate.
2. The number (#) of tests were just right.
3. There were too many tests.
4. I enjoyed participating in this study.
5. I disliked participating in this study.
6. I would recommend the study to a friend.
7. The # of study visits were just right.
8. There were too many study visits.

**Scale:** 1-Completely Disagree; 2- Disagree; 3- Neutral; 4-Agree; 5- Completely Agree

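### Aim 3 sets out to relate attrition to perceived suitability, fatigue and mood, but no planned analysis does so, and the visit-number statements are rated by completers only

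*Combined protocol and SAP*

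**What the plan says.** **Objective.** Aim 3 in Section 3.0 opens with "Explicate study attrition by perceived suitability of aspects the study design" and adds the relation of suitability to fatigue and mood. The Abstract says the results will be used to "examine feasibility in terms of study attrition relative to Veteran fatigue, mood, and Veteran reports of suitability". Three sub-hypotheses follow in Section 3.0: attrition does not differ by diagnosis (3i), perceptions of suitability are similar across diagnoses (3ii), and suitability is related to fatigue and mood (3iii).

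**Rating schedule (Section 5.1).** Study-Day 1 lists "Rating suitability of the number and types of tests 1-3". Study-Days 2 and 3 each list "Suitability ratings 1-3". Study-Day 4, the last visit of the main study, lists "Suitability rating 1-8". In Table 4, statement 7 is "The # of study visits were just right" and statement 8 is "There were too many study visits".

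**Analysis (Section 5.6).** Attrition is the share of participants lost after Study-Day 2 and after Study-Day 3. It is compared between stroke and TBI by chi-square. Mean ratings are compared between stroke and TBI by t-tests. Statements 1 to 3 are correlated with fatigue and mood, and the plan adds "correlations for average suitability indices 7 through 8 collected on Study-Day 4 (B4", set against fatigue and mood from the same day.

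**Withdrawal (Section 5.7).** Data collected before withdrawal are kept unless the participant revokes authorization. No rating at exit is described.

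**The concern.** Two gaps combine. The first is in the analysis: the link named in the Aim 3 heading and in the Abstract, between leaving the study and how suitable, tiring or distressing it was, is never estimated. The second is in the data: a Veteran who leaves after Day 2 or Day 3 because there are too many visits is never asked about the number of visits.

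The results are meant to inform a later within-subject cross-over study, where the number and length of visits is a central design choice. Days 2 and 3 last about 8 hours each, so dropout driven by burden is plausible. If the plan is followed as written, the designers of that study will have attrition rates by diagnosis and a set of ratings, with nothing connecting the two. Their information on visit number will come only from people who attended every visit.

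**Working it through.** **Inputs.** 48 enrolled, 42 required, 12% attrition (Section 5.6); the rating schedule and the persisting-effects (PE) timepoints B0 to B4 (Section 5.1); the 1-to-5 agreement scale (Table 4); the Aim 3 analyses (Section 5.6).

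**The plan's own figures.** At effect size 0.90, 80% power and two-sided 5% (assumed, because the sample-size paragraph gives no alpha), the t-based size is 20.4, hence 21 per group and 42 in total. Then 42 / (1 − 0.12) = 47.7, rounded up to 48. Both figures reproduce. Expected leavers: 48 × 0.12 = 5.76, about 6. Expected completers: 48 × 0.88 = 42.24, about 42. Share without a Day 4 rating: 6/48 = 12.5%.

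**What is collected, by visit.**

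| Visit | Statements 1–3 | Statements 4–8 | PE fatigue and mood |
|---|---|---|---|
| Day 1 | yes | no | – |
| Day 2 | yes | no | B0, B1 |
| Day 3 | yes | no | B2, B3 |
| Day 4 | yes | yes | B4 |

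A Veteran who leaves after Day 2 has two ratings of statements 1 to 3 and two PE batteries. One who leaves after Day 3 has three ratings and four batteries. Neither can have a rating of statements 4 to 8.

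**What each Aim 3 analysis uses.**

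| Analysis | Dropout | Rating | Fatigue or mood |
|---|---|---|---|
| 3i, chi-square by diagnosis | yes | no | no |
| 3ii, t-tests by diagnosis | no | yes | no |
| 3iii, statements 1–3: 5×(3×2) + 5×(3×5) = 105 correlations | no | yes | yes |
| 3iii, statements 7–8: (2×2) + (2×5) = 14 correlations | no | yes | yes |

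The correlation counts reproduce. No row uses dropout together with a rating, fatigue or mood.

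**Size of the completer effect.** Let m_c be the completers' mean and m_l the mean that leavers would have given. Then

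full-sample mean − m_c = [(42 m_c + 6 m_l)/48] − m_c = (6/48)(m_l − m_c) = 0.125 × gap.

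The documents give no rating data, so the gap is an assumption:

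| Leavers of 48 | Gap 1 | Gap 2 | Gap 4 (scale maximum) |
|---|---|---|---|
| 3 | 0.0625 | 0.125 | 0.25 |
| 6 (planned) | 0.125 | 0.25 | 0.50 |
| 12 | 0.25 | 0.50 | 1.00 |

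On the share agreeing that there were too many visits, if 10% of completers and all 6 leavers agreed (assumed, extreme), the full-sample share would be 0.10 × 42/48 + 6/48 = 21%, not 10%.

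**What a leaver-versus-completer comparison could show.** With 6 against 42, a two-sided 5% t-test has 52% power at a standardized difference of 0.90 and reaches 80% only at about 1.25 (1.71 with 3 leavers, 0.95 with 12). The half-width of a 95% interval in SD units is 2.013 × √(1/6 + 1/42) = 2.013 × 0.436 = 0.88. Such a comparison is descriptive only.

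**The case against.** The best defence is that 3i, 3ii and 3iii each have a matching analysis, and that 3iii answers the second half of the Aim 3 heading. This stands. The unmatched part is the heading's link between attrition and suitability, together with the Abstract's wording. It is nevertheless the stated purpose of the aim, and no sub-hypothesis covers it.

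Three stronger readings are tempting, and the documents do not support them.

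- A reader might infer that the whole feasibility answer comes from survivors. It does not. Attrition is computed on everyone at risk. Statements 1 to 3, one of which asks whether there were too many tests, are rated from Day 1, and fatigue and mood are measured from B0. Later leavers contribute to all of these, and Section 5.7 keeps their data.
- A reader might infer that the number of visits will look more acceptable than it is. Only *may* is justified. Section 5.1 lists stopping reasons unrelated to visit burden (shock, seizure activity, medication change, pregnancy), and Section 5.7 adds medical reasons, investigator decision and loss of funding.
- A reader might infer that dropout concentrated in one diagnosis would create or hide a stroke–TBI difference in 3ii unnoticed. That needs a rating SD, which the documents do not give. The extreme split, 6/24 against 0/24, would also show in 3i if dropout is pooled over visits: chi-square = 0.25² / [0.125 × 0.875 × (2/24)] = 6.86, p about 0.009 (Fisher p about 0.02). Splitting dropout by visit, as the plan does, weakens that signal.

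It can also be said that this is a pilot and that about six leavers cannot support inference. That is right, and it argues for description rather than for leaving the comparison out: feasibility is the pilot's own purpose and most of the data are already scheduled.

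**Conclusion.** The point holds in a limited form. Followed exactly as written, the plan leaves one stated objective, attrition in relation to suitability, fatigue and mood, without any analysis. Separately, statements 4 to 8 are rated by completers only. The visit-number part of 3ii and the 14 Day 4 correlations therefore describe about 42 of 48 Veterans, if attrition is the planned 12%.

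The absence of any overlap between counted attrition and visit-number ratings follows from the schedule and needs no assumption. The shift of 0.125 per point of gap assumes six leavers; the gap itself, in size and direction, is unknown. No treatment-effect estimate or safety decision is affected. The change is worth making because it is cheap and because the later cross-over study would rely on this information.

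**What to change.** 1. **Add a descriptive comparison to Aim 3 in Section 5.6.** Report the last available ratings of statements 1 to 3, and the last fatigue and mood scores, for Veterans who later left and for those who completed, with intervals and no formal test. State the visit each score comes from, so that a leaver's Day 2 or Day 3 score is set against completers' scores at the same visit. This needs SAP wording only.
2. **Ask statements 7 and 8 at the end of Study-Days 2 and 3 as well as on Day 4.** Adding them on Day 3 alone would still miss those who leave after Day 2.
3. **Report the Day 4 ratings of statements 4 to 8 as completer ratings**, including in 3ii and the 14 correlations, with the number of raters out of the number enrolled.

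The cost is two one-line items at two existing visits, the matching edit to the visit schedule, and a short analysis paragraph. The drawbacks are that early ratings of visit number are given before all visits are done, and that a Veteran who stops partway through a visit is still missed. A telephone rating at withdrawal would reach some of these, but it is a new procedure in a cognitively impaired group, some with surrogate consent, and is not proposed here.
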